4 TRIAL DESIGN

The trial is a pharmacodynamic study to determine the effect of aspirin dose modification on immune response, compared to control and compared between the presence and absence of potent P2Y₁₂ inhibition with ticagrelor. Healthy volunteers will receive either no aspirin (control group) or one of three doses of aspirin (aspirin lysine) with or without a loading dose of ticagrelor on the last day of the first medication period, as specified in this protocol, for 10-14 days. They will then receive E. coli endotoxin to induce an immune response. Serial measurements of inflammatory markers, cytokines, leucocyte function, prostanoids and platelet function will be taken over 6 hours. Bleeding time will be measured before endotoxin administration and 3 hours after it to assess haemostasis. After a washout period of at least 5 weeks, and not more than 18 weeks, subjects will then crossover to receive the same regimen of aspirin (aspirin lysine) (or no aspirin in the control group) without or with a loading dose of ticagrelor on the last day of the second medication period. The dose-dependent effects of aspirin and the impact of ticagrelor will be compared between the groups.

A total of 72 eligible subjects are planned to be randomised. There will be three regimens of aspirin (aspirin lysine) included in the study, in addition to a control group (no aspirin), each tested with and without a 180 mg loading dose of ticagrelor. Aspirin (aspirin lysine) 75 mg OD represents the current standard regimen in ACS and for primary and secondary prevention of cardiovascular disease. Aspirin (aspirin lysine) 20 mg BD

is a novel regimen hypothesised to provide a better profile of inflammatory and antithrombotic effect than 75 mg OD. Lastly, aspirin 300 mg OD represents a regimen commonly given after coronary artery bypass grafting.

Randomisation will be in a 1:1:1:1:1:1:1 fashion and managed by a commercially available service for this purpose, SealedEnvelope, with whom the sponsor will have a study-specific contract.

E. coli endotoxin will be administered at the end of each treatment period according to the protocol. Subjects will be recruited from the area local to the Northern General Hospital, Sheffield. For example, we will recruit members of staff and students from universities in Sheffield and from Sheffield Teaching Hospitals. Volunteers will be given as much time as they need to consider taking part in the study prior to signing informed consent.

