10 STATISTICS AND DATA ANALYSIS

10.1 Sample size calculation

In our group's previous study of endotoxaemia in 30 participants receiving ticagrelor, clopidogrel or placebo, we saw, after log transformation, a mean 2 hour post-endotoxin plasma TNF- α 1.88 pg/ml with a standard deviation of 0.410 pg/ml.

There is no available raw data and no reliable estimate of the means or standard deviations of the log transformed TNF- α values for any of the three aspirin doses using the same methods. However, a study using a different endotoxin regimen has shown that aspirin 80 mg OD (which is not expected to be significantly different in effect to 75 mg OD) increased peak plasma TNF- α by around 40% compared to those receiving no drug.

We have a clear hypothesis that increasing aspirin dose increases TNF- α , therefore a one-sided test will suffice.

We estimate that clinically-relevant differences in plasma TNF- α at 2 hours post-endotoxin between the dosing regimens might be a 20% increase with 20 mg BD vs. no aspirin, 40% increase with 75 mg OD vs. no aspirin and 60% with 300 mg OD vs. no aspirin, based on the raw data.

These assumptions provide the following sample size estimate:

Test significance level, α	0.050
Number of groups, G	4
Variance of means, $V=S(m_i-m)^2 / G$	0.031
Common standard deviation, s	0.410
Effect size, $D^2 = V/s^2$	0.1828
Power (%)	80
n per group	16

Therefore, when the sample size in each of the 4 groups is 16, a one-way analysis of variance will have 80% power to detect at the 0.050 level a difference in means characterised by a Variance of means, $V=\sum(\mu_i-\mu)^2 / G$ of 0.031, assuming that the common standard deviation is 0.410.

To allow for up to 10% drop-out, the sample size per group will be 18. Drop-outs will not be replaced but it is expected that there will be at least 16 per group after withdrawals.

This sample size calculation was performed by [name] CStat, Senior Consultant, Statistical Services Unit, University of Sheffield, to whom the investigators are grateful.

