BD, 75 mg OD, 300 mg OD, each without ticagrelor) and each corresponding DAPT regimen (control, 20 mg BD, 75 mg OD, 300 mg OD, each with ticagrelor 90 mg BD) by paired t-tests.

9. AUC of the graph of circulating leukocyte count over time following endotoxin administration (measured at 0, 0.5, 1, 1.5, 2, 3, 4 and 6 hours post-endotoxin) compared between each aspirin regimen (control, 20 mg BD, 75 mg OD, 300 mg OD, each without ticagrelor) and each corresponding DAPT regimen (control, 20 mg BD, 75 mg OD, 300 mg OD, each with ticagrelor 90 mg BD) by paired t-tests.
10. AUC of the graph of bleeding time following endotoxin administration (measured at 0 and 3 hours post-endotoxin) compared between each aspirin regimen (control, 20 mg BD, 75 mg OD, 300 mg OD, each without ticagrelor) and each corresponding DAPT regimen (control, 20 mg BD, 75 mg OD, 300 mg OD, each with ticagrelor 90 mg BD) by paired t-tests.
11. AUC of the graphs of platelet aggregation to arachidonic acid (0.3 and 1 mmol/L), collagen (4 and 16 µg/ml) and ADP (20 µmol/L) over time following endotoxin administration (measured at 0 and 3 hours post-endotoxin) compared between each aspirin regimen (control, 20 mg BD, 75 mg OD, 300 mg OD, each without ticagrelor) and each corresponding DAPT regimen (control, 20 mg BD, 75 mg OD, 300 mg OD, each with ticagrelor 90 mg BD) by paired t-tests.

And to model the effects of all variables (considering parallel groups):

12. Plasma TNF-α over time following endotoxin administration (measured at 0, 0.5, 1, 1.5, 2, 3, 4 and 6 hours post-endotoxin) compared between each aspirin regimen (control, 20 mg BD, 75 mg OD, 300 mg OD, each without ticagrelor) and each corresponding DAPT regimen (control, 20 mg BD, 75 mg OD, 300 mg OD, each with ticagrelor 90 mg BD) with a mixed three-way ANOVA with aspirin-dose and presence or absence of ticagrelor as between-subjects factors and timepoint as a within-subject factor.
13. Plasma IL-6 over time following endotoxin administration (measured at 0, 0.5, 1, 1.5, 2, 3, 4 and 6 hours post-endotoxin) compared between each aspirin regimen (control, 20 mg BD, 75 mg OD, 300 mg OD, each without ticagrelor) and each corresponding DAPT regimen (control, 20 mg BD, 75 mg OD, 300 mg OD, each with ticagrelor 90 mg BD) with a mixed three-way ANOVA with aspirin-dose and presence or absence of ticagrelor as between-subjects factors and timepoint as a within-subject factor.

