8. AUC of the graph of serum PGE2 over time following endotoxin administration (measured at 0, 0.5, 1, 1.5, 2, 3, 4 and 6 hours post-endotoxin) compared between each aspirin regimen (control, 20 mg BD, 75 mg OD, 300 mg OD, each without ticagrelor) and each corresponding DAPT regimen (control, 20 mg BD, 75 mg OD, 300 mg OD, each with ticagrelor 90 mg BD) by paired t-tests.
9. AUC of the graph of circulating leukocyte count over time following endotoxin administration (measured at 0, 0.5, 1, 1.5, 2, 3, 4 and 6 hours post-endotoxin) compared between each aspirin regimen (control, 20 mg BD, 75 mg OD, 300 mg OD, each without ticagrelor) and each corresponding DAPT regimen (control, 20 mg BD, 75 mg OD, 300 mg OD, each with ticagrelor 90 mg BD) by paired t-tests.
10. AUC of the graph of bleeding time following endotoxin administration (measured at 0 and 3 hours post-endotoxin) compared between each aspirin regimen (control, 20 mg BD, 75 mg OD, 300 mg OD, each without ticagrelor) and each corresponding DAPT regimen (control, 20 mg BD, 75 mg OD, 300 mg OD, each with ticagrelor 90 mg BD) by paired t-tests.
11. AUC of the graphs of platelet aggregation to arachidonic acid (0.3 and 1 mmol/L), collagen (4 and 16 µg/ml) and ADP (20 µmol/L) over time following endotoxin administration (measured at 0 and 3 hours post-endotoxin) compared between each aspirin regimen (control, 20 mg BD, 75 mg OD, 300 mg OD, each without ticagrelor) and each corresponding DAPT regimen (control, 20 mg BD, 75 mg OD, 300 mg OD, each with ticagrelor 90 mg BD) by paired t-tests.

And to model the effects of all variables (considering parallel groups):

12. Plasma TNF- $\alpha$  over time following endotoxin administration (measured at 0, 0.5, 1, 1.5, 2, 3, 4 and 6 hours post-endotoxin) compared between each aspirin regimen (control, 20 mg BD, 75 mg OD, 300 mg OD, each without ticagrelor) and each corresponding DAPT regimen (control, 20 mg BD, 75 mg OD, 300 mg OD, each with ticagrelor 90 mg BD) with a mixed three-way ANOVA

with aspirin-dose and presence or absence of ticagrelor as between-subjects factors and timepoint as a within-subject factor.

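### The three-way ANOVAs (section 10.3.3, second list, items 12–20) call ticagrelor a between-subjects factor although it is crossed over, and do not say which visits enter

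*Protocol*

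**What the plan says.** Protocol section 4 describes a crossover on ticagrelor within a fixed aspirin regimen: after washout, "subjects will then crossover to receive the same regimen of aspirin (aspirin lysine"), without or with the ticagrelor dose, whichever was not given before. All eight sequences in section 7.3 pair one period with ticagrelor and one without.

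Section 10.3.3 contains two numbered lists. Items 12–20 of the second list are meant to model all factors together. They use a mixed three-way ANOVA with "aspirin-dose and presence or absence of ticagrelor as between-subjects factors and timepoint as a within-subject factor". The SAP repeats this: "with aspirin-dose and presence or absence of ticagrelor as between-subjects factors". The lead-in adds, in brackets, that parallel groups are considered. It does not restrict the analysis to one period. No term links a participant's two visits and none represents period.

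Other parts of the plan treat the design differently:
- Items 1–11 of the same list compare with and without ticagrelor by paired t-tests.
- The early-termination models in section 10.6 have participant as a random effect and period as a fixed effect.
- Section 10.7 admits to the pharmacodynamic set only participants who complete both endotoxin days.

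**The concern.** A factor that changes within every participant has been declared as one that varies only between participants. If both visits are entered under that declaration, 72 people are analysed as 144 independent records. The error term is then too small for aspirin, which varies between people, and too large for ticagrelor and for aspirin by ticagrelor, which vary within people.

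The second aim in section 7 is to show whether adding ticagrelor modifies the effects of aspirin dose. That is an interaction question, and items 12–20 are the only analyses in the full plan that test the interaction. Their p-values also decide whether Bonferroni pairwise comparisons follow, so an inflated aspirin F test would open that step too often.

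**Working it through.** **1. The plan's own figure.** Section 10.1 states that "a one-way analysis of variance will have 80% power to detect at the 0.050 level a difference in means". Log means ln(1, 1.2, 1.4, 1.6) give V = 0.0307. With s = 0.410, D² = 0.0307/0.410² = 0.1828. For n = 16 in each of 4 groups the noncentrality is 4 × 16 × 0.1828 = 11.70 on 3 and 60 df, and power is 80.2%; n = 15 gives 77.1%. Then 16/0.9 = 17.8, rounded up to 18 per group, and 4 × 18 = 72. The figure reproduces. It concerns the primary one-way ANOVA, which uses one record per participant.

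**2. Inputs for items 12–20.** There are n = 18 per aspirin regimen and two visits each, hence 144 records and 8 × (18 − 1) = 136 error df if every record counts as a separate person. Let s² be the variance of a visit-level value and r the correlation between one person's two visits. The documents do not give r, so I assume 0.3, 0.5 and 0.7.

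**3. Expected mean squares with both visits entered, no true effects.**
- Error: s².
- Aspirin: s²(1 + r).
- Ticagrelor and aspirin × ticagrelor: s²(1 − r).

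The true rejection rate is therefore approximately the tail of F beyond the critical value divided by (1 + r) or (1 − r). The 5% critical values are 2.671 (3, 136 df) and 3.911 (1, 136 df). At r = 0.5:
- Aspirin: 2.671/1.5 = 1.781, giving 15.4%.
- Ticagrelor: 3.911/0.5 = 7.821, giving 0.6%.
- Interaction: 2.671/0.5 = 5.342, giving 0.2%.

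**4. Power.** Choose the effect for which the correct within-participant test (68 error df) has 80% power. The noncentrality is 8.08 for ticagrelor (1 df) and 11.55 for the interaction (3 df). Planned power is the noncentral F tail, with 136 error df, beyond the critical value divided by (1 − r).

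**5. Period 1 only.** Expected numbers are 72/8 = 9 per cell, with 8 × (9 − 1) = 64 error df. The variance of the ticagrelor contrast is 2s²/36, against 2s²(1 − r)/72 in the crossover. The noncentrality is therefore multiplied by (1 − r)/2. Because section 7.3.1 specifies simple randomisation, 9 per cell is an expectation, not a guarantee.

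| | r = 0.3 | r = 0.5 | r = 0.7 |
|---|---|---|---|
| Both visits: aspirin type I error | 10.9% | 15.4% | 19.9% |
| Both visits: ticagrelor type I error | 2.0% | 0.6% | 0.04% |
| Both visits: interaction type I error | 1.2% | 0.2% | <0.1% |
| Both visits: ticagrelor power (correct test 80%) | 68% | 52% | 23% |
| Both visits: interaction power (correct test 80%) | 62% | 38% | 7% |
| Period 1 only: ticagrelor power | 38% | 29% | 19% |
| Period 1 only: interaction power | 34% | 25% | 16% |

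The standard error used for ticagrelor is too large by 1/√(1 − r), which is 1.20, 1.41 and 1.83.

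**6. Checks.** A simulation with 18 per group, 8 timepoints and 20,000 replicates gave aspirin type I error of 0.109, 0.158 and 0.204 and ticagrelor power of 0.68, 0.52 and 0.23. With ticagrelor handled within participant, type I error was 4.9–5.1% for both main effects at every r from 0 to 0.8. Using 16 per group changes the main-effect results by no more than 0.003.

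**The case against.** The strongest reply is that the bracketed reference to parallel groups means period 1 only. In a trial described as a hybrid of parallel-group and crossover, that reading makes the between-subjects label literally correct and keeps type I error at 5%. It cannot be excluded. However, no period restriction is written, and the pharmacodynamic set requires both endotoxin days. It would also discard half the data, so one reading is invalid and the other wasteful.

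A second reply is that other planned analyses cover most of the ground. This stands for the main effects. Ticagrelor is tested by paired t-tests within each regimen, and aspirin by one- and two-way ANOVAs within a single ticagrelor condition. If the trial stops early, the section 10.6 models apply. It does not stand for the interaction: the paired tests run separately by regimen, and the section 10.6 models list main effects only. For the interaction the error is conservative, so the risk is a missed effect, not a false claim.

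A reader might infer that the ticagrelor tests lose most of their power. The documents give no correlation to support that. With both visits entered, more than half the power is lost only above r of about 0.59 (from 80%) or 0.67 (from 90%). A reader might also infer that every aspirin test in these models is anti-conservative. That is shown only for the main effect with both visits entered. For aspirin by time it depends on the covariance pattern. In a separate simulation, a constant person-level shift left the error at 4.7–5.0%. Differences in peak height inflated it, but it was already 9% at r = 0 because of non-sphericity, which is a different issue.

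**Conclusion.** The factor is misdeclared in the current text of both documents, and the records to be analysed are not stated. With both visits entered, the aspirin main-effect test rejects too often for any positive correlation, by about two to four times the nominal rate for r from 0.3 to 0.7. The ticagrelor and interaction tests reject too rarely. With period 1 only, the tests are valid but ticagrelor and interaction power fall by more than half from r = 0.3 upwards. All power figures rest on an assumed r and on an effect for which the correct test has 80% power.

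The problem is confined to secondary items. It would be wrong to read it as a threat to the primary result, which uses one visit per participant. It should be fixed before analysis, chiefly because the interaction has no other test in the full plan.

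**What to change.** In items 12–20, in both documents:
- State that both visits enter and that ticagrelor is a within-subject factor.
- Use the mixed model already written in section 10.6 (participant random effect, period fixed effect). Add aspirin × ticagrelor, and timepoint with its treatment interactions where there are repeated timepoints.
- Where a visit has repeated timepoints, add a participant-by-period random effect. Omit it for item 14 (CRP change), which has one value per visit, so that effect could not be separated from the residual.

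The cost is amended wording and different model code. No new data are needed. The sample size does not change, because it was set on the primary one-way ANOVA.

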3.3 Outcome measures/endpoints

Primary endpoint/outcome

The primary endpoint will be plasma TNF- α at 2 hours post-injection of 2 ng/kg endotoxin compared between participants receiving no IMP, aspirin (Aspirin lysine) 20 mg BD, aspirin (Aspirin lysine) 75 mg OD and aspirin (Aspirin lysine) 300 mg OD.

Secondary endpoints/outcomes

1. Plasma levels from 0 to 6 hours after endotoxin administration, of TNF- α
2. Plasma levels from 0 to 6 hours after endotoxin administration, of plasma TNF- α
3. Change in serum CRP from 0 to 6 hours after endotoxin administration
4. Leukocyte count, from 0 to 6 hours after endotoxin administration
5. Serum TXB₂ from 0 to 6 hours after endotoxin administration

6. Serum PGE₂, from 0 to 6 hours after endotoxin administration
7. AUC of the graph, from 0 to 6 hours after endotoxin administration, of urine PGI-M
8. AUC of the graph, from 0 to 3 hours after endotoxin administration, of bleeding time
9. Mean platelet aggregation responses to arachidonic acid (AA), collagen and adenosine diphosphate (ADP), from 0 to 6 hours after endotoxin administration.

Secondary endpoints will be compared between:

1. Participants receiving no IMP, aspirin (aspirin lysine) 20 mg BD, aspirin (aspirin lysine) 75 mg OD and aspirin (aspirin lysine) 300 mg OD.
2. Participants receiving no aspirin and a 180 mg loading dose of ticagrelor, aspirin (aspirin lysine) 20 mg BD plus a 180 mg loading dose of ticagrelor, aspirin (aspirin lysine) 75 mg OD plus a 180 mg loading dose of ticagrelor, and aspirin (aspirin lysine) 300 mg OD plus a 180 mg loading dose of ticagrelor.
3. Participants receiving no IMP and a 180 mg loading dose of ticagrelor.
4. Participants receiving aspirin (aspirin lysine) 20 mg BD, and aspirin (aspirin lysine) 20 mg BD plus a 180 mg loading dose of ticagrelor.
5. Participants receiving aspirin (aspirin lysine) 75 mg OD, and aspirin (aspirin lysine) 75 mg OD plus a 180 mg loading dose of ticagrelor.
6. Participants receiving aspirin (aspirin lysine) 300 mg OD, and aspirin (aspirin lysine) 300 mg OD plus a 180 mg loading dose of ticagrelor.

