- Collect unused study medication and perform drug accountability check (sachet/pill count)
- Infusion of 250 ml 0.9% saline over 30 minutes
- 23 ml venous blood at 60 minutes after last dose of oral antiplatelet medication or equivalent time if not receiving IMP during period 1 (just before endotoxin administration)

0 hour (time of endotoxin injection)

- Continuous cardiac monitoring starts
- *E.coli* endotoxin 2 ng/kg intravenously administered over 1 minute
- Vital signs at 5, 15 and 30 minutes post-endotoxin
- Continuous IV infusion of 250 ml 0.9% saline over 1 hour
- 14 ml venous blood sample at 30 minutes post endotoxin

1 hour post-endotoxin injection

- Vital signs at 1 hour and 1.5 hours post endotoxin injection
- Continuous IV infusion of 250 ml 0.9% saline over 1 hour
- 14 ml venous blood sample at 1 hour post endotoxin
- Urine sample at 1 hour post endotoxin
- 14 ml venous blood sample at 1½ hours post endotoxin

2 hours post-endotoxin injection

- Vital signs at 2 hours post endotoxin

- Continuous IV infusion of 250 ml 0.9% saline over 1 hour
- 23 ml venous blood sample at 2 hours post endotoxin
- Urine sample at 2 hours post endotoxin

3 hours post-endotoxin injection

- Vital signs at 3 hours post endotoxin
- 23 ml venous blood sample at 3 hours post endotoxin
- Bleeding time measurement at 3 hours post endotoxin

4 hours post-endotoxin injection

- Vital signs at 4 hours post endotoxin
- 14 ml venous blood sample at 4 hours post endotoxin
- Urine sample at 4 hours post endotoxin

6 hours post-endotoxin injection

- Vital signs at 6 hours post endotoxin
- 14 ml venous blood sample at 6 hours post endotoxin
- Urine sample at 6 hours post endotoxin
- Continuous cardiac monitoring ends

Visit 8 (Period 2, 1 day after visit 6)

- Telephone follow-up for adverse events
- Facility to convert to in-person visit if any concerns raised

Visit 9 (Period 2, 10 to 14 days after visit 6)

- Telephone follow-up for adverse events

Study investigations will be performed at the following time points:*

*Baseline refers to visit 2, and the pre- and post-endotoxin samples are to be taken during both experimental periods.

- **Inflammatory markers and cytokines**
- TNF- α : Baseline, pre-last medication dose, pre-endotoxin and 0.5, 1, 1.5, 2, 3, 4 and 6 hours post-endotoxin
- IL-6: Baseline, pre-last medication dose, pre-endotoxin and 0.5, 1, 1.5, 2, 3, 4 and 6 hours post-endotoxin
- CRP: Baseline, pre-endotoxin and 6 hours post-endotoxin

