10.3.3 Secondary outcome analysis

Secondary analyses will be as follows:

Between aspirin dose regimens

1. Plasma TNF- α over time following endotoxin administration (measured at 0, 0.5, 1, 1.5, 2, 3, 4 and 6 hours post-endotoxin) assessed between aspirin groups (control vs. 20 mg BD vs. 75 mg OD vs. 300 mg OD, without ticagrelor) by two-way mixed ANOVA with treatment as a between-subjects factor and timepoint as a within-subjects factor.
2. Plasma IL-6 at 2 hours following endotoxin administration assessed between aspirin groups (control vs. 20 mg BD vs. 75 mg OD vs. 300 mg OD, without ticagrelor) by one-way ANOVA with treatment as a factor.
3. Plasma IL-6 over time following endotoxin administration (measured at 0, 0.5, 1, 1.5, 2, 3, 4 and 6 hours post-endotoxin) assessed between aspirin groups (control vs. 20 mg BD vs. 75 mg OD vs. 300 mg OD, without ticagrelor) by two-way mixed ANOVA with treatment as a between-subjects factor and timepoint as a within-subjects factor.
4. Change in serum CRP over time following endotoxin administration (measured at 0 and 6 hours post-endotoxin) assessed between aspirin groups (control vs. 20 mg BD vs. 75 mg OD vs. 300 mg OD, without ticagrelor) by one-way ANOVA.
5. Serum TXB₂ over time following endotoxin administration (measured at 0, 0.5, 1, 1.5, 2, 3, 4 and 6 hours post-endotoxin) assessed between aspirin groups (control vs. 20 mg BD vs. 75 mg OD vs. 300 mg OD, without ticagrelor) by two-way mixed ANOVA with treatment as a between-subjects factor and timepoint as a within-subjects factor.
6. Urinary PGI-M (measured at 0, 2, 4 and 6 hours, each adjusted for [divided by] urinary creatinine) over time following endotoxin administration assessed between aspirin groups (control vs. 20 mg BD vs. 75 mg OD vs. 300 mg OD, without ticagrelor) by two-way mixed ANOVA with treatment as a between-subjects factor and timepoint as a within-subjects factor.
7. Serum PGE₂ over time following endotoxin administration (measured at 0, 0.5, 1, 1.5, 2, 3, 4 and 6 hours post-endotoxin) assessed between aspirin groups (control vs. 20 mg BD vs. 75 mg OD vs. 300 mg OD, without ticagrelor) by two-way mixed ANOVA with treatment as a between-subjects factor and timepoint as a within-subjects factor.

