14. Change in serum CRP over time following endotoxin administration (measured at 0 and 6 hours post-endotoxin) compared between each aspirin regimen (control, 20 mg BD, 75 mg OD, 300 mg OD, each without ticagrelor) and each corresponding DAPT regimen (control, 20 mg BD, 75 mg OD, 300 mg OD, each with ticagrelor 90 mg BD) with a mixed three-way ANOVA with aspirin-dose and presence or absence of ticagrelor as between-subjects factors and timepoint as a within-subject factor.
15. Serum TXB₂ over time following endotoxin administration (measured at 0, 0.5, 1, 1.5, 2, 3, 4 and 6 hours post-endotoxin) compared between each aspirin regimen (control, 20 mg BD, 75 mg OD, 300 mg OD, each without ticagrelor) and each corresponding DAPT regimen (control, 20 mg BD, 75 mg OD, 300 mg OD, each with ticagrelor 90 mg BD) with a mixed three-way ANOVA with aspirin-dose and presence or absence of ticagrelor as between-subjects factors and timepoint as a within-subject factor.

16. Urinary PGI-M (measured at 0, 2, 4 and 6 hours, each adjusted for [divided by] urinary creatinine) over time following endotoxin administration compared between each aspirin regimen (control, 20 mg BD, 75 mg OD, 300 mg OD, each without ticagrelor) and each corresponding DAPT regimen (control, 20 mg BD, 75 mg OD, 300 mg OD, each with ticagrelor 90 mg BD) with a mixed three-way ANOVA with aspirin-dose and presence or absence of ticagrelor as between-subjects factors and timepoint as a within-subject factor.
17. Serum PGE₂ over time following endotoxin administration (measured at 0, 0.5, 1, 1.5, 2, 3, 4 and 6 hours post-endotoxin) compared between each aspirin regimen (control, 20 mg BD, 75 mg OD, 300 mg OD, each without ticagrelor) and each corresponding DAPT regimen (control, 20 mg BD, 75 mg OD, 300 mg OD, each with ticagrelor 90 mg BD) with a mixed three-way ANOVA with aspirin-dose and presence or absence of ticagrelor as between-subjects factors and timepoint as a within-subject factor.
18. Circulating leukocyte count over time following endotoxin administration (measured at 0, 0.5, 1, 1.5, 2, 3, 4 and 6 hours post-endotoxin) compared between each aspirin regimen (control, 20 mg BD, 75 mg OD, 300 mg OD, each without ticagrelor) and each corresponding DAPT regimen (control, 20 mg BD, 75 mg OD, 300 mg OD, each with ticagrelor 90 mg BD) with a mixed three-way ANOVA with aspirin-dose and presence or absence of ticagrelor as between-subjects factors and timepoint as a within-subject factor.

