19. Bleeding time following endotoxin administration (measured at 0 and 3 hours post-endotoxin) compared between each aspirin regimen (control, 20 mg BD, 75 mg OD, 300 mg OD, each without ticagrelor) and each corresponding DAPT regimen (control, 20 mg BD, 75 mg OD, 300 mg OD, each with ticagrelor 90 mg BD) with a mixed three-way ANOVA with aspirin-dose and presence or absence of ticagrelor as between-subjects factors and timepoint as a within-subject factor.
20. Platelet aggregation to arachidonic acid (0.3 and 1 mmol/L), collagen (4 and 16 µg/ml) and ADP (20 µmol/L) over time following endotoxin administration (measured at 0 and 3 hours post-endotoxin) compared between each aspirin regimen (control, 20 mg BD, 75 mg OD, 300 mg OD, each without ticagrelor) and each corresponding DAPT regimen (control, 20 mg BD, 75 mg OD, 300 mg OD, each with ticagrelor 90 mg BD) with a mixed three-way ANOVA with aspirin-dose and presence or absence of ticagrelor as between-subjects factors and timepoint as a within-subject factor.

For all endpoints (primary and secondary) tested with ANOVA, pairwise comparisons with Bonferroni correction will be used to explore relationships further where the prespecified test suggests significant differences between the groups (p<0.05).

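### Item 14 of the all-variables list (10.3.3) puts a timepoint factor on a single CRP change per visit, so the model cannot be fitted as written and the test to be read is not named

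*Protocol*

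**What the plan says.** Protocol 3.3 defines the CRP endpoint as "Change in serum CRP from 0 to 6 hours after endotoxin administration". The sampling schedule in 7.7 is "CRP: Baseline, pre-endotoxin and 6 hours post-endotoxin", where baseline means visit 2. Each endotoxin day therefore supplies two CRP values and one change.

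Section 10.3.3 numbers its items in two runs: 1 to 21, then 1 to 20. The second run contains the paired comparisons (1 to 11) and the models of all variables (12 to 20). CRP appears four times:

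- First run, items 4 (without ticagrelor) and 15 (with ticagrelor): "Change in serum CRP over time following endotoxin administration (measured at 0 and 6 hours post-endotoxin) assessed between aspirin groups", each by one-way ANOVA with no timepoint factor.
- Second run, item 5: the same change, with versus without ticagrelor, by paired t-tests.
- Second run, item 14: "Change in serum CRP over time following endotoxin administration (measured at 0 and 6 hours post-endotoxin) compared between each aspirin regimen", analysed "with a mixed three-way ANOVA with aspirin-dose and presence or absence of ticagrelor as between-subjects factors and timepoint as a within-subject factor".

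The rule that closes 10.3.3 is that "pairwise comparisons with Bonferroni correction will be used to explore relationships further where the prespecified test suggests significant differences between the groups". It does not say which term of a three-way ANOVA it means. The SAP repeats all of this under the same numbers.

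Section 10.6 has a separate CRP model for use if the trial stops early (item 3). It is a linear mixed model of the CRP change with patient as random effect; aspirin dose, ticagrelor and period as fixed effects; and baseline as covariate. It has no timepoint factor.

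**The concern.** A change between two times already uses up the time dimension. Once it is the response, each visit contributes one number and nothing is left for a timepoint factor to distinguish. Item 14 looks like wording carried over from the serially measured markers. For bleeding time and aggregation, the plan uses one summary (AUC) in the paired comparisons (items 10 and 11) and returns to the values at each time once timepoint enters the model (items 19 and 20). Among items 12 to 20, only item 14 keeps a single summary together with timepoint.

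An analyst must therefore repair the item, either by dropping timepoint or by entering the raw 0 h and 6 h values. In the second case the model has main effects and interactions that answer different questions, and the plan does not choose between them. The follow-up rule speaks of differences between groups, which is most naturally read as the main effect. Two analysts could report different quantities and different p-values from the same item. Because the investigators are unblinded (7.4), the choice could also be made after the data are seen.

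**Working it through.** **The plan's own figure.** Section 10.1 sizes only the primary TNF-α comparison; CRP has no sample-size figure. From natural logs of 1, 1.2, 1.4 and 1.6, the variance of means is V = 0.0307 (stated 0.031). Then D² = 0.0307/0.410² = 0.1828, as stated. With 4 groups of 16 and α = 0.05, noncentral F power is 80.2% (77.1% at 15). Allowing for drop-out, 16/0.9 = 17.8, which rounds up to 18. The figure reproduces and does not depend on item 14.

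**Step 1: item 14 as written.** The response is one change per visit. Timepoint has 1 level, so its degrees of freedom are 1 − 1 = 0. There are also 0 within-subject residual degrees of freedom in the item's own layout. Timepoint and its interactions cannot be estimated.

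**Step 2: raw values entered instead.** Let δ0 and δ6 be the difference between two treatment groups at 0 h and 6 h.

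- Difference in change: δ6 − δ0.
- Main-effect difference (mean of the two times): (δ0 + δ6)/2.
- Treatment-by-timepoint interaction, with two times: δ6 − δ0, which is the difference in change.

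If δ0 = 0, the main effect is δ6/2, half the difference in change. If δ0 is not 0, the factor is no longer one half.

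**Step 3: numerical check.** One balanced data set was simulated in the layout that item 14 declares (4 aspirin × 2 ticagrelor cells, 16 records per cell, every record a separate subject). The true 0 h means were equal and the true 300 mg versus control difference in change was 3.00.

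| Analysis | Estimate, 300 mg vs control | Aspirin F (3, 120 df) |
|---|---|---|
| Change score | 2.95 | 31.18 |
| Raw values, aspirin × timepoint | same contrast as the change score | 31.18 |
| Raw values, aspirin main effect | 1.54 | 11.69 |

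The main effect is not exactly 2.95/2 because the sample had a chance 0 h difference of about 0.07 (1.543 − 2.948/2).

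**Step 4: does halving cost power?** Let s0 and s6 be the SDs at the two times and ρ their correlation.

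- Var(change) = s0² + s6² − 2ρ·s0·s6.
- Var(mean) = (s0² + s6² + 2ρ·s0·s6)/4.

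With δ0 = 0, the noncentrality of the main effect relative to the change analysis is

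(s0² + s6² − 2ρ·s0·s6)/(s0² + s6² + 2ρ·s0·s6).

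The factor ½ in the estimate is offset by the factor ¼ in the variance; only the correlation term remains. For s0 = s6 and ρ = 0.5 the ratio is (2 − 1)/(2 + 1) = 0.333.

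The documents give no CRP SD or correlation, so the table below uses assumed values. It takes a four-group comparison with 16 per group, with the change analysis set at 80.2% power by borrowing D² = 0.1828. Entries are the power of the main effect.

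| ρ | s0 = s6 | s0 = 0.5·s6 | s0 = 0.2·s6 |
|---|---|---|---|
| 0 | 80.2% | 80.2% | 80.2% |
| 0.3 | 51.1% | 57.0% | 69.5% |
| 0.5 | 33.0% | 41.6% | 61.8% |
| 0.7 | 18.7% | 28.2% | 54.1% |
| 0.9 | 8.6% | 17.5% | 46.6% |

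These figures apply only if raw values are entered and only the main effect is read.

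**The case against.** The best defence is that item 14 names both measuring times as well as a timepoint factor. An analyst could sensibly read this as two raw values per visit, and the model then runs. Its aspirin-by-timepoint and ticagrelor-by-timepoint terms carry the full effect on the change, with the same F statistic as the change-score ANOVA. The prespecified model would then contain the right test. This stands, and it limits the point: what is lacking is a response that fits the model and a named term.

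A reader might also infer that CRP has no other sound analysis, or that a real CRP effect would usually be reported as absent. The documents do not support either. Items 4 and 15 of the first run test aspirin dose on the change. Item 5 of the second run tests ticagrelor on it. The early-termination model in 10.6 uses both factors without timepoint, and that route is live because visits were halted and stopping criteria set.

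Finally, this is one of 21 + 20 = 41 listed secondary analyses in a study that the protocol itself calls exploratory. That bears on priority. It does not remove the contradiction.

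**Conclusion.** Item 14 is wrongly specified in both documents. With the endpoint as defined, timepoint has 0 degrees of freedom and the ANOVA cannot be fitted. This follows from the text alone and needs no assumption.

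The consequence of the raw-value repair is conditional. The main effects are half the difference in change when groups are equal at 0 h, while the timepoint interactions lose nothing. Because the plan names no term and the follow-up rule points to group differences, the main effect could be read and an effect on the change missed.

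It is tempting to say that raw values halve the effect and so lose power. That goes too far: halving concerns the main effects only, and by itself costs no power. In the illustration, the power of the main effect ranges from 80.2% (zero correlation) down to 8.6% (equal SDs, correlation 0.9), against 80.2% for the change. All of these rest on assumed SDs and correlations. The primary analysis, the sample size and the CRP tests in items 4, 5 and 15 are not affected.

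**What to change.** In item 14 of the protocol and the SAP, delete the closing clause on timepoint. Analyse the one CRP change per visit by aspirin dose (between participants), ticagrelor (within participants) and their interaction, with participant as a random effect. This is in line with the early-termination CRP model in 10.6, whose period and baseline terms can be carried over; the aspirin-by-ticagrelor interaction has to be added, since 10.6 does not list it.

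The error structure must be written out in the item. It should not be borrowed from the other all-variables models, because items 12 to 20 take "presence or absence of ticagrelor as between-subjects factors and timepoint as a within-subject factor", whereas every sequence in 7.3 gives each participant one period with ticagrelor and one without.

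Alternatively, keep the raw 0 h and 6 h values, say so in place of the change, and prespecify the treatment-by-timepoint interactions as the tests, with both visits of a participant linked in the model.

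Either option costs about one line in each document and needs no new data.
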